### 1.5 Known and Potential Benefits and Risks to Patients

Complete information may be found in the IB provided to each investigator. Each investigator must become familiar with all information in the IB before commencing this study.

The potential benefits to participating patients with acute postsurgical pain following abdominoplasty are (1) that they may experience a reduction in acute postoperative pain as a result of treatment with INL-001, (2) that they will understand they are contributing to the scientific knowledge that may lead to expansion of the treatment options for patients' acute postsurgical pain, and (3) because INL-001 is implanted (not injected) into the surgical site, accidental intravascular injection/surgical site infiltration that often leads to bupivacaine's most serious potential central nervous system (CNS) and CV systemic toxicities may be prevented.

The potential risks of study participation include those associated with exposure to INL-001 per the FDA-approved labeling and the risks of medical evaluation, including venipuncture and other risks associated with the required medical procedures.

Because individual patient factors may impact the safety of an amide local anesthetic such as bupivacaine, there is a potential risk for severe life-threatening adverse effects associated with the local administration of bupivacaine. Therefore, INL-001 should be administered in a setting where trained personnel and equipment are available to promptly treat patients who show evidence of CNS or CV toxicity. Monitoring cardiovascular and neurologic status, as well as vital signs, should be performed during and after placement of INL-001.

Allergic-type reactions are rare and may occur as a result of sensitivity to bupivacaine or to other formulation ingredients. These reactions are characterized by signs of urticaria, pruritus, erythema, angioedema (including laryngeal edema), tachycardia, sneezing, nausea, vomiting, dizziness, syncope, excessive sweating, elevated temperature, and possibly anaphylactoid-like symptoms (including severe hypotension). Cross-sensitivity among members of the amide-type local anesthetic group has been reported.

Innocoll

Clinical Study Protocol With Amendment 02

Study INN-CB-024

Controlled Study-Postsurgical Analgesia

---

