### **3 STUDY DESIGN**

#### **3.1 General Study Design**

This is a multicenter, randomized, double-blind, placebo-controlled efficacy and safety study of the INL-001 (bupivacaine HCl) implant, at 300 mg, in patients following abdominoplasty. On the day of surgery (study day 1), eligible patients will be randomly assigned to treatment in a 1:1 ratio to receive either INL-001 (three 100-mg implants containing a total dose of 300 mg of bupivacaine HCl) or 3 placebo collagen implants. Patients will then undergo abdominoplasty under general anesthesia and have INL-001 or placebo implanted intraoperatively.

The duration of study participation for each patient will be a maximum of 75 ( $\pm 3$ ) days, consisting of a screening period (up to 45 days before surgery), an inpatient period (preoperative, intraoperative, immediately postoperative) of approximately 4 days, and an outpatient follow-up period (up to 30 days [ $\pm 3$  days] after treatment) including an end-of-study visit. Efficacy assessments will be made through 72 hours after treatment (after implant placement). Posttreatment (time measured from Time 0 [placement of first implant]) safety assessments will be made throughout the study after the informed consent form (ICF) is signed, and as specifically scheduled through 72 hours posttreatment, on day 7 ( $\pm 1$  day) (telephone), on day 15 ( $\pm 3$  days) (clinic visit), and on day 30 ( $\pm 3$  days) (clinic visit). Unless the investigator determines further hospitalization is necessary, the patient will be discharged on the day occurring 72 hours (day 4) after surgery.

During the screening period, all patients will provide informed consent and undergo eligibility and other screening and safety assessments (medical history including review of prior medications, physical examination, urine drug screen, serum pregnancy test for women of childbearing potential, clinical laboratory tests [hematology, chemistry, urinalysis], vital signs measurement, and 12-lead electrocardiography [ECG]). Vital signs include body temperature, pulse, systolic and diastolic blood pressure, respiration rate, and oxygen saturation measured by pulse oximetry. The reason(s) a patient does not meet screening criteria will be recorded, if applicable. Recording of adverse events and concomitant medication use will commence once a patient signs the ICF.

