### **3.5.2 Day of Surgery (Day 1)**

#### **3.5.2.1 Immediate Preoperative Period**

The following will take place:

- study-drug kit number assigned after preoperative assessments (patient enrolled)
- demographics/medical history (update)
- inclusion/exclusion criteria
- UDS (results available before study-drug kit number assignment)
- urine pregnancy test (for women of childbearing potential/results available before study-drug kit number assignment)
- prior medications (including opioids and other analgesic medication)
- vital signs (body temperature, pulse, systolic and diastolic blood pressure, respiration rate, and oxygen saturation measured by pulse oximetry)
- adverse events

Innocoll

Clinical Study Protocol With Amendment 02

Study INN-CB-024

Controlled Study-Postsurgical Analgesia

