#### 7.5 Vital Signs

Vital signs, including body temperature, pulse, systolic and diastolic blood pressure, respiration rate, and oxygen saturation, will be measured/recorded at screening, preoperatively, and at the following posttreatment time points: 0.5 hours ( $\pm 5$  minutes); 1, 2, 4 hours ( $\pm 15$  minutes); 8, 12 hours ( $\pm 2$  hours); 24, 48, 72 hours ( $\pm 4$  hours) prior to discharge; day 15 ( $\pm 3$  days); and day 30 ( $\pm 3$  days) (see [Table 1](#)).

Oxygen saturation will be monitored by pulse oximetry during the inpatient study period. Oxygen saturation will be recorded at the individual time points listed above. Pulse oximeter alarms should be set according to clinic standards, with oxygen desaturation that occurs in concordance with the delay period and the specified limits recorded as an adverse event. Patients should be evaluated to ensure proper pulse oximeter placement and to ensure desaturation is not due to patient movement or device-related issues.

All vital sign results outside the reference ranges will be judged by the investigator as belonging to one of the following categories:

- abnormal and not clinically significant
- abnormal and clinically significant

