### **7.7 Electrocardiography**

A standard 12-lead ECG will be performed locally (by a physician [ie, the investigator or subinvestigator]) and recorded (after the patient has been supine for at least 5 minutes) at screening and on day 30 ( $\pm 3$  days) (see [Table 1](#)). All ECG recordings will be identified with the patient number, date, and time of the recording.

All ECG results outside of the reference ranges should be evaluated and will be judged as belonging to one of the following categories:

- abnormal and not clinically significant
- abnormal and clinically significant

Any ECG finding that is judged as clinically significant (except at the screening visit) will be considered an adverse event, recorded on the source documentation and on the CRF, and monitored as described in [Section 7.1.2](#).

Innocoll

Clinical Study Protocol With Amendment 02

Study INN-CB-024

Controlled Study-Postsurgical Analgesia

---

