## **9.6 Safety and Tolerability Analysis and Planned Method of Analysis**

### **9.6.1 Safety and Tolerability Analysis**

Safety variables include assessment of adverse events, clinical laboratory test results, vital signs measurements (including body temperature, pulse, systolic and diastolic blood pressure, respiration rate, and oxygen saturation measured by pulse oximetry), ECG findings, surgical wound grading, and concomitant medications. These analyses will be conducted for the safety population. No formal statistical tests will be performed on safety evaluations.

Adverse events will be coded using Medical Dictionary for Regulatory Activities (MedDRA), version 18 or later. The number and percentage of patients with adverse events will be displayed for each treatment group by system organ class (SOC) and preferred term. Summaries in terms of severity and relationship to study treatment will also be provided. Serious adverse events will be summarized separately in a similar fashion. In the case of multiple occurrences of the same adverse event for the same patient, the patient will be counted only once for each SOC and preferred term. All adverse events and serious adverse events will be listed by patient.

Adverse events collected from the assessments for systemic bupivacaine toxicity and wound healing will each be presented both as part of the adverse events overall and summarized separately. Additionally, the counts and percentages of patients in category of the Southampton Wound Grading Scale will be reported at each time point where it is collected.

Clinical laboratory test results, vital signs measurements, and any other appropriate quantitative safety data will be presented descriptively by treatment group at each time point for the baseline (screening) and postbaseline evaluations, as well as change from baseline, using descriptive statistics (number, mean, SD, median, minimum, and maximum).

ECG data including RR, PR, QRS, and QTc intervals will be summarized descriptively.

Innocoll

Clinical Study Protocol With Amendment 02

Study INN-CB-024

Controlled Study-Postsurgical Analgesia

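### Vital-sign change is measured from screening although a day-1 preoperative value exists, and Section 7.5 lacks the adverse event recording rule given for laboratory, physical examination and ECG findings

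*Protocol*

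**What the plan says.** **Baseline.** Protocol Section 9.6.1 states in one sentence that laboratory tests, vital signs and other numerical safety measures "will be presented descriptively by treatment group at each time point for the baseline (screening) and postbaseline evaluations, as well as change from baseline". The same sentence says that these summaries are made "using descriptive statistics (number, mean, SD, median, minimum, and maximum"). Section 3.1 describes participation as "consisting of a screening period (up to 45 days before surgery"). Section 7.5 states that vital signs "will be measured/recorded at screening, preoperatively, and at the following posttreatment time points: 0.5 hours" and onward to day 30. Section 3.5.2.1 lists the same set among the procedures immediately before surgery on day 1: "vital signs (body temperature, pulse, systolic and diastolic blood pressure, respiration rate, and oxygen saturation measured by pulse oximetry").

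**Rating and recording.** Section 7.5 says: "All vital sign results outside the reference ranges will be judged by the investigator as belonging to one of the following categories", the two categories being abnormal without and abnormal with clinical significance. The section ends there. Its only adverse event instruction concerns oxygen desaturation detected by the oximeter alarms. Section 7.7 uses the same two categories for ECGs and then adds: "Any ECG finding that is judged as clinically significant (except at the screening visit) will be considered an adverse event". Sections 7.4.1 and 7.6 contain an equivalent rule for laboratory tests and physical examination.

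**Why vital signs matter here.** Section 1.5 says: "Monitoring cardiovascular and neurologic status, as well as vital signs, should be performed during and after placement of INL-001". Section 7.1.6 names systemic bupivacaine toxicity as one of two safety areas of interest.

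**The concern.** The two points are separate, and each is something the protocol states itself.

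First, change from baseline should describe what happened to the patient after implantation. A value taken on the morning of surgery does that better than one that may be more than six weeks old. Conditions can also differ between the two dates. Exclusion criterion (e) bars alpha-adrenergic agonists, systemic steroids, anticonvulsants and monoamine oxidase inhibitors in the 10 days before surgery, so a patient could be screened while taking such a drug and treated after stopping it. Screening suits laboratory tests, which have no later pretreatment value. Vital signs share that sentence and inherit a baseline that does not suit them.

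Second, the missing rule in Section 7.5 affects what is entered during the trial. A clinically significant fall in blood pressure or pulse may be rated as such and still not be entered as an adverse event. One investigator may apply the general definition to it and another may not, across up to 8 centers. A later analysis plan can change a baseline, but it cannot recover adverse events that were never recorded.

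Scheduled vital signs carry weight in this trial because no 12-lead ECG is scheduled between screening and day 30. The median time to peak bupivacaine concentration in the hernia pharmacokinetic study was 3.03 hours (Section 1.4.2). The 14-item toxicity checklist has no pulse, blood pressure or rhythm item.

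**Working it through.** The protocol gives no figure to reproduce on this point. The check sets its sections side by side, with one small illustration.

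**Step 1: which pretreatment values exist (Table 1 and Sections 3.5.1, 3.5.2.1, 7.4, 7.5, 7.7).**

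| Measure | Screening | Day 1, preoperative | Latest pretreatment value |
|---|---|---|---|
| Laboratory tests | yes | no | screening |
| 12-lead ECG | yes | no | screening |
| Vital signs | yes | yes | day 1 |

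Screening is the right baseline for the first two rows and not the nearest one for the third.

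**Step 2: what the protocol says to do with a clinically significant result.**

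| Section | Rated for clinical significance | Stated to be an adverse event if clinically significant |
|---|---|---|
| 7.4.1 Laboratory tests | yes | yes (screening results that preclude entry excepted) |
| 7.6 Physical examinations | yes | yes (screening excepted) |
| 7.7 Electrocardiography | yes | yes (screening excepted) |
| 7.5 Vital signs | yes | no; desaturation only |

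Section 7.5 is the exception, for the one measure in this table that is scheduled repeatedly from 0.5 to 72 hours.

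**Step 3: size of the baseline effect (illustration).** If baseline and later readings have the same SD and correlation rho, then

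SD of change / raw SD = sqrt(2 × (1 − rho)).

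The protocol gives no correlations, so these are assumed:

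- rho = 0.4: sqrt(1.2) = 1.10
- rho = 0.5: sqrt(1.0) = 1.00
- rho = 0.7: sqrt(0.6) = 0.77
- rho = 0.8: sqrt(0.4) = 0.63

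If the older value correlates at 0.4 to 0.5 and the same-day value at 0.7 to 0.8, the SD of change falls from 1.00–1.10 to 0.63–0.77 of the raw SD. If the two correlations are equal, nothing is gained in spread. The gain depends on the nearer value being the better predictor, which is plausible but not shown in the protocol.

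**The case against.** A reader might infer that individual cardiovascular toxicity is hidden because vital signs are analyzed only as group statistics. It is true that means would not show it. With 180 patients per arm, two patients with an assumed 50 mmHg fall move the mean by 2 × 50 / 180 = 0.56 mmHg. The standard error of the difference is SD × sqrt(2/180), or 1.05 to 2.11 mmHg for assumed SDs of 10 to 20, so the shift is only 0.53 to 0.26 standard errors. The documents nevertheless do not support the inference:

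- Section 9.6.1 also plans the minimum and maximum, where one extreme fall would ordinarily appear, although without a count of patients.
- Section 7.1.1 defines an adverse event to include an unfavorable physical sign, and Section 7.1.2.4 requires all adverse events to be recorded.
- Section 9.6.1 counts adverse events by arm, lists them by patient, and summarizes separately those from the toxicity assessment.
- Systemic toxicity, once determined, is recorded as an adverse event and triggers an ECG and a blood sample (Section 3.1).

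Nor is a missing table of patients with out-of-range or clinically significant values a finding. Section 9 defers further analysis detail to the SAP, which is not at hand.

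On the baseline, it can fairly be said that both arms use the same reference, so the randomized comparison is not biased. Section 9.6.1 plans no formal safety tests, so extra spread costs no power. Raw values are presented as well. Early readings may be dominated by anesthesia and surgery, and an awake preoperative value may reflect anxiety. These arguments limit the size of the point. They do not give a reason to prefer the older value.

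On recording, the general definition does apply to vital signs. It leaves unexplained why three parallel sections state the rule and Section 7.5 does not.

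**Conclusion.** Both points stand, at modest size. Section 9.6.1 makes an explicit choice of screening as baseline, so this is not a gap left to the SAP, and for vital signs a nearer pretreatment value is already collected. Section 7.5 is out of line with Sections 7.4.1, 7.6 and 7.7, so entry of a clinically significant pulse or blood pressure change as an adverse event rests on individual application of the general definition.

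The consequences are change scores that are probably noisier than necessary, and possibly uneven recording between centers. The extent of the first depends on correlations that the protocol does not give. The second cannot be quantified from the protocol. The treatment comparison is not biased by the baseline choice, and no efficacy result, power or sample size figure is affected. Correcting both is worthwhile because it is nearly free. The recording point should come first, because it cannot be repaired after the data are collected.

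**What to change.** 1. In Section 9.6.1, define the vital-sign baseline as the last value before Time 0: the day-1 preoperative value, or screening if that is missing. Keep screening as the baseline for laboratory tests and ECG. Screening vital signs can remain as a supportive listing.
2. Reconcile Section 7.5 with the adverse event recording rule in Sections 7.4.1, 7.6 and 7.7, so that the protocol states how a vital sign rated clinically significant after baseline is recorded. This concerns recording only, not patient management.

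The cost is one definition and one sentence, with no new measurements or visits. The adverse event count may rise slightly. The preoperative value may carry some presurgical anxiety, which should be equal in both arms.

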### 9.6.2 Planned Method of Analysis

The mITT analysis set (see [Section 9.5](#)) will be used for all efficacy analyses. In general, summaries will be presented overall and by surgery type.

The efficacy analysis will estimate the SPI24, SPI48, and SPI72.

### 9.7 Sensitivity Analysis

The following 2 sensitivity analyses will be performed:

- To investigate the impact of the assumed period of efficacy for the rescue medication, a shorter period of 2 hours following oxycodone and acetaminophen rescue medication administration, and 1 hour following morphine will be used in the imputation algorithm.
- To investigate the impact of the choice of reasons for discontinuation when imputing from the distribution of worst values, 2 additional analyses will be performed: the first will include data from patients who withdraw for “other” or “unknown” reasons in the group receiving values imputed from the distribution of worst value. (Additional items may also be included and detailed in the SAP.) The second will impute from the distribution of worst values for **all** withdrawn patients.

### 9.8 Multiple Comparisons and Multiplicity

The key secondary efficacy variables will be tested sequentially each at the 0.05-level to control the overall Type-I error rate. Specifically, each key secondary variable will be tested in order. The next key secondary variable will be tested if the prior secondary variable comparison is statistically significant. The order is as follows:

- SPI48
- proportion of patients who are opioid free posttreatment through 24 hours
- proportion of patients who are opioid free posttreatment through 48 hours
- SPI72
- proportion of patients that are opioid free posttreatment through 72 hours

### 9.9 Planned Interim Analysis

An interim analysis will be performed when approximately 50% of the initially planned population is evaluable with respect to efficacy. This interim analysis will be performed by unblinded personnel separate from those responsible for the conduct and analysis of the study; all decisions will be made on the basis of SPI24, SPI48 and/or SPI72. An independent committee will review the data and recommend to the sponsor one of the following:

- increase the sample size by up to 180 patients
- keep the current sample size and continue

SPI24 will be evaluated first. If the conditional power for SPI24 is at or over 90% with the current sample size, then the committee will base recommendations on SPI48 and/or SPI72. If the conditional power for SPI24 is between 20% and less than 90%, the committee will recommend increasing the sample size. This increase will be chosen by adding blocks of 10

Innocoll

Clinical Study Protocol With Amendment 02  
Study INN-CB-024

Controlled Study-Postsurgical Analgesia

patients with the goal of selecting the minimum number of patients such that the SPI24 conditional power is raised to at least 90%.

In the case that SPI24 conditional power is at or over 90%, SPI48 will be evaluated as above, ie, no change will be made if conditional power is at or over 90%; otherwise, the smallest increase that would raise its power over 90% will be chosen.

Likewise, if SPI48 conditional power is at or over 90%, SPI72 will be evaluated as above, ie, no change will be made if conditional power is at or over 90%; otherwise, the smallest increase that would raise its power over 90% will be chosen.

At each step, the subsequent SPI will also be checked. If its conditional power can be raised to over 90% with no more than an additional 30 patients beyond what the current step suggests, that will be the recommendation returned by the committee (again, in blocks of 10 patients). For example, if SPI24 is over 90% conditional power, but SPI48 required an increase of 38 patients and SPI72 required an increase of 63 patients, the recommended increase would be 70 patients (increases may only be done in blocks of 10 patients).

For SPI24, SPI48, and SPI72, if the conditional power at the current sample size is over 20% and the maximum increase of 180 patients falls short of raising the conditional power to at least 90%, the committee will recommend an increase of 180 patients. No further information will be provided to the sponsor beyond this recommendation and the sponsor may choose to ignore the recommendation and leave the sample size unchanged.

Conditional power will be calculated using the following formula (Mehta and Pocock 2011):

$$CP(Z_1, \check{n}_2) = 1 - \Phi\left(\frac{Z_\alpha\sqrt{n_2} - Z_1\sqrt{n_1}}{\sqrt{\check{n}_2}} - \frac{Z_1\sqrt{\check{n}_2}}{\sqrt{n_1}}\right)$$

where  $Z_1$  is the value of the Z score at the interim,  $n_1$  is the actual sample size at the interim,  $n_2$  is the total planned sample size (360 patients), and  $\check{n}_2$  is the total planned sample size minus the actual sample size at the interim.

Due to the speed of enrollment, it is possible full enrollment of the initial sample size will be achieved prior to the completion of the interim analysis. A small overrun may be possible in this scenario, if the committee does not recommend an increase.

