To account for the interim analysis and potential sample size increase, the method of [Cui et al 1999](#) will be employed. For the final analysis and resulting p-value, the data will be split for those patients included in the interim analysis and those not included in the interim analysis; data from these groups will be analyzed completely independently, then combined using the inverse normal method to test the null hypotheses that there is no difference between the treatment groups:

$$Z_1 = \Phi^{-1}(1 - p_1)$$

$$\text{and } Z_2 = w_1 Z_1 + w_2 \Phi^{-1}(1 - p_2)$$

where:

$Z_1$ =the Z statistic for the first stage

$Z_2$ =the combination test statistic at the end of the second stage

$w_i$ =the weighting applied for each associated Z statistic

$p_1$ =the first stage p-value

$p_2$ =the second-stage p-value based on second-stage participants

For maximum statistical efficiency, the weights are defined prospectively according to the square root of the planned proportion of participants in the 2 stages, relative to the preplanned total enrollment of 360 patients, as  $w_i = \sqrt{0.5}$ . The calculation of these weights is fixed and will not be changed due to unblinded data; likewise, in the case of deviations from the planned proportions due to enrollment overrun (see interim analysis section below), the weights will remain fixed.

The key secondary efficacy variables include:

- SPI from Time 0 through 48 hours (SPI48)
- proportion of patients who are opioid free posttreatment through 24 hours
- proportion of patients who are opioid free posttreatment through 48 hours
- SPI from Time 0 through 72 hours (SPI72)
- proportion of patients who are opioid free posttreatment through 72 hours

An approach identical to the primary efficacy analysis will be used for each of the continuous key secondary variables and the same statistics will be presented. For key secondary outcomes of proportions, each proportion, the difference, and 95% confidence intervals (CIs) will be reported; the difference will be tested with the 2-proportion Z test (with Cui-Hung-Wang [CHW] method

Innocoll

Clinical Study Protocol With Amendment 02

Study INN-CB-024

Controlled Study-Postsurgical Analgesia

applied to account for the interim analysis). In the case of low counts (any expected cell count  $\leq 5$ ), a Fisher's Exact test will be used; p-values will be transformed to an equivalent Z for applying the CHW method.

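### The conditional-power formula in Protocol Section 9.9 has no term for the sample-size increase it must choose, and the natural repair does not match the fixed-weight final test

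*Protocol*

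**What the plan says.** Section 9.9 sets the interim at about half of the planned population and allows the committee to "increase the sample size by up to 180 patients". For the primary variable the rule is: "If the conditional power for SPI24 is between 20% and less than 90%, the committee will recommend increasing the sample size". On the amount it says "This increase will be chosen by adding blocks of 10" patients, with the goal of "selecting the minimum number of patients such that the SPI24 conditional power is raised to at least 90" per cent. The same search then applies to SPI48 and SPI72. If even 180 more patients fall short of 90%, 180 is recommended.

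The section gives one formula, CP(Z1, ň2). Its symbols are the interim Z score Z1, the actual interim size n1, the total n2 (set at 360), and ň2, which "is the total planned sample size minus the actual sample size at the interim". Z_α appears without a value.

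Section 9.5 fixes the final test. The two stages are analysed separately and combined by the inverse normal method with weights √0.5 each. On those weights it says: "The calculation of these weights is fixed and will not be changed due to unblinded data".

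**The concern.** A rule that searches for the smallest sufficient increase needs a formula in which the increase appears. Here n2 and ň2 are both tied to the planned 360, so the user must decide where to put the enlarged size. The protocol does not say, and the two obvious choices give different answers.

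Neither choice matches the planned test. With fixed weights, the value that the second-stage Z must exceed depends only on Z1, the weights and Z_α. A larger second stage raises the expected second-stage Z but does not move that boundary. In the printed formula ň2 is also the divisor of the boundary term, so an enlarged ň2 lowers the boundary and overstates the power.

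At stake is how many of up to 180 further patients are recruited, and whether the conditional power aimed at is the one obtained. Section 5.11 confines the committee to calculating the adjustment under prespecified rules, so the formula should not need interpreting once unblinded results are in hand.

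**Working it through.** **Inputs**
- Planned total 360, cap 180, blocks of 10, zone 20% to below 90%: Section 9.9.
- n1 = 180: assumed, as exactly half of 360.
- Weights w1 = w2 = √0.5, unchanged by the increase: Section 9.5.
- Z_α = 1.96: assumed. Section 9.8 states 0.05 without a side. Section 9.1 gives power of at least 66% for an effect size of 0.25 with 180 per group. Two-sided 0.05 gives Φ(0.25 × √(180/2) − 1.96) = Φ(0.412) = 66.0%, which reproduces that figure. One-sided 0.05 would give 76.6%.

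Section 9.9 states no conditional power (CP) value to reproduce.

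**Step 1. The formula as defined.** CP = 1 − Φ(b − d), where b = (Z_α√n2 − Z1√n1)/√ň2 is the boundary and d = Z1√ň2/√n1 is the drift. With n2 = 360 and n1 = ň2 = 180, b = 1.96√2 − Z1 = 2.772 − Z1 and d = Z1, so CP = Φ(2·Z1 − 2.772). This is 59.0% at Z1 = 1.5 and 79.6% at Z1 = 1.8, with no term for an increase. CP is 20% at Z1 = (2.772 − 0.842)/2 = 0.965 and 90% at Z1 = (2.772 + 1.282)/2 = 2.027.

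**Step 2. CP of the planned test.** The test rejects when √0.5·Z1 + √0.5·Z(stage 2) > 1.96, that is, when Z(stage 2) > (1.96 − √0.5·Z1)/√0.5 = 2.772 − Z1. If the interim trend continues, Z(stage 2) has mean Z1√(m*/n1), where m* = 360 + increase − n1. So

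CP = 1 − Φ[(Z_α − w1·Z1)/w2 − Z1√(m*/n1)].

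With no increase this equals step 1 exactly at n1 = 180, so the zone limits are right. Two million simulated second stages at Z1 = 1.5 and +180 gave 80.3%, against 80.2% by formula.

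**Step 3. One case in full, Z1 = 1.8.**
- *Planned test:* boundary 2.772 − 1.8 = 0.972. At +100 the drift is 1.8√(280/180) = 2.245 and CP = Φ(1.273) = 89.9%. At +110 the drift is 2.285 and CP = Φ(1.313) = 90.5%. The answer is +110.
- *ň2 enlarged in both terms:* at +70 the boundary falls to (37.188 − 24.150)/√250 = 0.825 and the drift is 2.121, so the formula reports Φ(1.297) = 90.3%. With the true boundary it is Φ(2.121 − 0.972) = 87.5%.
- *n2 enlarged as well:* this is the CP of a pooled, unweighted test. It first reaches 90% at +140: boundary (1.96√500 − 24.150)/√320 = 1.100, drift 2.400, Φ(1.300) = 90.3%.

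**Step 4. Across the zone** (+180 where 90% is not reached)

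| Z1 | CP at 360 | Both terms: increase (CP reported; true CP) | Planned test: increase (CP) | Pooled: increase |
|---|---|---|---|---|
| 1.5 | 59.0% | +180 (88.9%; 80.2%) | +180 (80.2%) | +180 |
| 1.6 | 66.6% | +150 (90.3%; 84.0%) | +180 (86.2%) | +180 |
| 1.7 | 73.5% | +110 (90.5%; 86.1%) | +170 (90.3%) | +180 |
| 1.8 | 79.6% | +70 (90.3%; 87.5%) | +110 (90.5%) | +140 |
| 1.9 | 84.8% | +40 (90.5%; 89.0%) | +60 (90.7%) | +80 |
| 2.0 | 89.0% | +10 (90.4%; 90.0%) | +10 (90.0%) | +20 |

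The both-terms version first reports 90% at +180 when Z1 is about 1.53: boundary 1.96 − 1.53/√2 = 0.878, drift 1.53√2 = 2.164, Φ(1.286) = 90.1%. Its chosen block drops to +170 by Z1 = 1.55: boundary (37.188 − 20.795)/√350 = 0.876, drift 2.161, Φ(1.285) = 90.1%. The planned test needs Z1 of 1.679 before +180 reaches 90%.

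With one-sided 0.05 the pattern is the same. At Z1 = 1.6 the both-terms version picks +80 (true CP 88.4%), the planned test +110 and the pooled version +150.

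**The case against.** The strongest defence is that the intention is clear. The notation makes ň2 an argument of the function. The block search, and the worked example in which SPI48 needs 38 more patients and SPI72 needs 63, presuppose a power that rises with the increase. A reader might infer from the definitions that conditional power never moves, so that every result in the zone yields +180, even Z1 = 2.0 where +10 suffices. The search and the example rule that out as a likely outcome. The literal text shows a defective definition, not what the committee would do.

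Other limits also stand:
- From Z1 of about 0.97 to 1.53, roughly half of the zone on the Z scale, both substituted versions and the correct formula recommend +180. The gap of 88.9% against 80.2% at Z1 = 1.5 changes nothing, because the sponsor receives only the recommendation.
- At Z1 = 1.6 a reader might infer a loss of 6 points against 90%. The correct formula cannot reach 90% there either. The loss is 86.2% − 84.0% = 2.2 points and 30 patients.
- 90% is a goal, not a guarantee. The 30-patient look-ahead to the next SPI and the sponsor's freedom to ignore the recommendation also shape the final number.
- A reader might fear an inflated type I error. The fixed weights prevent that, whatever increase is chosen.
- The charter cited in Section 5.11, or the SAP, may hold a working formula. Neither is shown, and neither would correct the protocol's text.

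The defence does not remove the main point: carrying out the evident intention by enlarging ň2 gives the power of a different test.

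**Conclusion.** The point holds, within bounds. The printed definitions leave the increase out of the formula, and neither natural substitution gives the conditional power of the test in Section 9.5. Enlarging ň2 alone picks too few patients for Z1 between about 1.53 and just under 2.0. At the tabulated values from 1.6 to 1.9 the shortfall is 20 to 60 patients, and true conditional power is 84.0% to 89.0%. Enlarging n2 as well picks too many, for example 30 extra at Z1 = 1.8 and 20 extra at 1.9.

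This is an error of sizing, not of validity. The zone limits are unaffected at n1 = 180, and so is the type I error. The figures assume n1 = 180, Z_α = 1.96 and continuation of the interim trend, as the protocol's formula does. They cover one SPI at a time, without the look-ahead. It should be fixed before the interim analysis.

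**What to change.** Replace the formula in Section 9.9, and in the interim committee's charter, with

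CP = 1 − Φ[(Z_α − w1·Z1)/w2 − Z1√(m*/n1)],

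where w1 = w2 = √0.5, Z_α = 1.96 is stated, and m* = 360 + increase − n1. State that m* is the only term that varies in the search over blocks of 10, and that the same formula serves SPI24, SPI48 and SPI72.

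The change needs one line of text and no new data. It is not free in patients. Relative to the both-terms reading, the correct formula recommends 20 to 60 more at the tabulated values from 1.6 to 1.9, within the existing cap of 180. Relative to the pooled reading it recommends fewer at Z1 = 1.7 to 2.0.
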